Caution is advised when considering the concomitant use of the following medications:

- Medications known to prolong QT or QTcF intervals.
- Strong inhibitors or inducers of P-glycoprotein and concomitant drugs that target serotonin 5HT_{2B}R are to be avoided with the exception of drugs that are considered absolutely essential for the care of the subject.
- Treatment with concomitant drugs that are strong inhibitors of CYP3A should be avoided with the exception of antibiotics, antifungals and antivirals that are used as standard of care to prevent or treat infections. If CYP3A inhibitors are used concomitantly, subjects should be closely monitored for AEs.

Precaution is advised in the use of gilteritinib (ASP2215) with concomitant drugs that are substrates of breast cancer resistance protein, since the transporter has been shown to be inhibited by gilteritinib (ASP2215) in in vitro studies.

Duration of Treatment:

Subjects will be treated until they no longer derive clinical benefit in the judgment of the treating physician, have unacceptable toxicity, undergo hematopoietic stem cell transplantation (HSCT), or meet 1 of the discontinuation criteria; whichever occurs first.

Definition of Dose Limiting Toxicity:

In phase 1, a DLT is defined as any of the following events that occur within the observation period (cycle 1/day 1 through cycle 1/day 28) and that is considered to be possibly or probably related to study regimen. In phase 2, the DLT observation period is the first treatment cycle (cycle 1/day 1 through cycle 1/day 28).

- Confirmed Hy's law case
- Any Grade ≥ 3 non-hematologic or extramedullary toxicity with the following exceptions:
 - Anorexia or fatigue
 - Grade 3 nausea and/or vomiting if not requiring tube feeding or TPN, or diarrhea if not requiring or prolonging hospitalization that can be managed to grade ≤ 2 with standard antiemetic or antidiarrheal medications used at prescribed dose within 7 days of onset
 - Grade 3 mucositis that resolved to grade ≤ 2 within 7 days of onset
 - Grade 3 fever with neutropenia, with or without infection*
 - Grade 3 infection*
 - Grade 3 infusion-related toxicity, if successfully managed and resolves within 72 hours.

*Toxicities are excluded only if the event is an expected direct complication of cytopenias due to the active underlying leukemia.

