7.1 Sample Size

This is an open-label, single arm study. No interim analysis and 1 final analysis are planned.

Phase 1

The sample size in phase 1 is based on 3+3 design and not based on power calculation.

Phase 2

Simon's 2-stage design [Simon, 1989] will be used in the study to evaluate the efficacy in terms of CRc rate for the selected combination dose level of gilteritinib and atezolizumab. The null hypothesis that the true CRc rate is 50% will be tested against a 1-sided alternative. In the first stage, the CRc of 22 subjects will be evaluated. If there are 11 or fewer subjects with CRc from these 22 subjects by the end of cycle 2, the study will be stopped. Otherwise, 27 additional subjects will be accrued for a total of 49 subjects evaluable for calculation of CRc rate. The null hypothesis will be rejected if 32 or more subjects with CRc are observed in the 49 subjects by the end of cycle 2. This design yields a 1-sided type I error rate of 0.025 and power of 80% when the true CRc rate is 70%. The sample size was calculated in East[®] Version 6.4.

Bayesian Posterior Probability for Safety Monitoring in Phase 2:

A Bayesian posterior probability will be used for safety monitoring during the whole treatment period. Subjects in phase 1 and phase 2 cohorts who complete the DLT observation period or experience DLTs will be included in the model-fitting process to provide the complete safety information. The DLT rate will be reviewed as the last subject of each cohort of 7 DLT-evaluable subjects completes the first treatment cycle. The estimated DLT rates based on the Bayesian beta-binomial model will be provided for safety monitoring in the dose expansion cohort. If the DLT rate for the expanded dose level is equal or higher than 20% with a posterior probability of 80%, then the enrollment to the expansion cohort will be paused and the safety will be reassessed by the DEC. If the reassessment warrants, enrollment to the expansion cohort may be continued at the current dose level or 1 lower dose level. Safety evaluation will be conducted separately for induction, consolidation and maintenance phases.

With a non-informative prior, Beta(1,1) distribution, the numbers of DLTs for each cohort of 7 DLT-evaluable subjects, which trigger the enrollment pause for toxicities review, are listed in the following [table](#):

DLT-evaluable Subjects	Number of DLTs
7	3
14	4
21	6
28	8
35	9
42	11
49	12

DLT: dose-limiting toxicity

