10.2 Other Study Organization

A DEC consisting of sponsor representatives and investigators will convene once a dose level cohort completes the DLT observation period and the data are available for review.

Additional details regarding responsibilities, membership requirements and safety review time points will be included in the DEC Plan.

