6.2.2 Definition of MTD

MTD is defined as the highest dose level where no more than one subject out of six eligible subjects has experienced DLT during the DLT observation period.

6.2.3 Bayesian Posterior Probability for Safety Monitoring in Phase 2

A Bayesian posterior probability will be used for safety monitoring during the whole treatment period. Subjects in phase 1 and phase 2 cohorts who complete the DLT observation period or experience DLTs will be included in the model-fitting process to provide the complete safety information. The estimated DLT rates based on the Bayesian beta-binomial model will be provided for safety monitoring in the dose expansion cohort. If the DLT rate for the expanded dose level is equal or higher than 25% with a posterior probability of 80%, then the enrollment to the expansion cohort will be paused and the safety will be reassessed by the DEC. If the reassessment warrants, enrollment to the expansion cohort may be continued at the current dose level or 1 lower dose level. Safety evaluation will be conducted separately for induction, consolidation and maintenance phases.

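### The phase 2 DLT pause is checked only at the end of each block of seven, with no rule to pause enrollment when the block's trigger count is reached earlier

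*Protocol*

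**What the plan says.** Protocol 7.1, repeated in the synopsis, pauses enrollment when the posterior probability that the DLT rate is at least 20% reaches 80%. The schedule is: "The DLT rate will be reviewed as the last subject of each cohort of 7 DLT-evaluable subjects completes the first treatment cycle". The model is stated as "With a non-informative prior, Beta(1,1) distribution", and a table gives "the numbers of DLTs for each cohort of 7 DLT-evaluable subjects, which trigger the enrollment pause for toxicities review": 3, 4, 6, 8, 9, 11 and 12 DLTs at 7, 14, 21, 28, 35, 42 and 49 evaluable subjects.

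On who is counted: "Subjects in phase 1 and phase 2 cohorts who complete the DLT observation period or experience DLTs will be included in the model-fitting process". The synopsis sets the phase 2 DLT period at the 28 days of cycle 1. Protocol 10.2 says the DEC "will convene once a dose level cohort completes the DLT observation period and the data are available for review" and leaves further review time points to a DEC Plan. Protocol 10.1 states that a monitoring committee does not apply.

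SAP 6.2.3 repeats the consequence, "then the enrollment to the expansion cohort will be paused and the safety will be reassessed by the DEC", but sets the threshold at 25% and gives neither schedule nor table.

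**The concern.** A subject with a DLT is evaluable by definition, and later subjects cannot lower a count. If the first three phase 2 subjects all have DLTs, the trigger of 3 at 7 is met whatever happens to subjects 4 to 7. Nothing in the text stops those four from being enrolled, or holds enrollment while the seventh completes 28 days. The same can happen later: 2 DLTs in the first 7 and 2 more by subject 9 fix the trigger of 4 at 14, with five subjects of the block still to enter.

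At stake is avoidable exposure to a regimen whose enrollment pause is already determined. This is the only quantitative toxicity rule in phase 2, and it follows a phase 1 of at most 12 subjects.

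**Working it through.** **1. Reproduce the table.** After x DLTs in n subjects the posterior is Beta(1+x, 1+n−x). The trigger is the smallest x with Pr(rate ≥ 0.20) ≥ 0.80.

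| n | Trigger | Posterior at trigger | One DLT fewer |
|---|---|---|---|
| 7 | 3 | 0.944 | 0.797 |
| 14 | 4 | 0.836 | 0.648 |
| 21 | 6 | 0.867 | 0.733 |
| 28 | 8 | 0.892 | 0.790 |
| 35 | 9 | 0.832 | 0.716 |
| 42 | 11 | 0.865 | 0.771 |
| 49 | 12 | 0.814 | 0.711 |

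All seven stated counts are right at 20%. Only the timing of the check is in question.

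**2. Is the criterion met mid-block?** The same number of DLTs in fewer subjects gives a higher posterior. At 3 of 3 it is Beta(4, 1): 1 − 0.2⁴ = 0.998, against 0.944 at 3 of 7. At 4 of 9 it is Beta(5, 6): 0.967, against 0.836 at 4 of 14.

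**3. Largest overrun within a block.** Carry in the highest count that did not pause at the previous look and let every new subject have a DLT. In block 1 the third subject reaches 3, leaving 7 − 3 = 4. In block 2, with 2 carried in, the second new subject reaches 4, leaving 7 − 2 = 5. Over the seven blocks the maximum is 4, 5, 4, 4, 5, 4 and 5.

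**4. Exact enumeration, subjects taken in sequence, phase 2 only.** If m more DLTs are needed when a block opens, the m-th falls on the block's k-th subject with probability C(k−1, m−1) pᵐ (1−p)ᵏ⁻ᵐ, and the overrun is 7 − k.

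| True DLT rate | P(pause) | Trigger met before block's last subject, given pause | Mean overrun, given pause | Expected subjects at pause (49 if none): block look → early trigger |
|---|---|---|---|---|
| 20% | 0.478 | 70% | 1.54 | 34.2 → 33.5 |
| 30% | 0.910 | 75% | 1.77 | 19.1 → 17.5 |
| 40% | 0.996 | 81% | 2.01 | 11.6 → 9.6 |

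Check at 30%: 0.910 × 1.77 = 1.6, the drop from 19.1 to 17.5. P(pause) is the same under both timings, because a count that reaches the trigger mid-block is still there at the look.

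**5. Add calendar time.** Step 4 omits enrollment during the last subject's 28 days; it also ignores that some subjects have already entered when the deciding DLT occurs. The documents give no accrual rate, so 1 to 4 per month is an assumption, with random (Poisson) entry and DLT times uniform over 28 days. Extra subjects enrolled between the deciding DLT and the block look, given a pause (20,000 simulated trials per scenario):

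| True DLT rate | 1 per month | 4 per month |
|---|---|---|
| 20% | about 1.9 | about 3.0 |
| 30% | about 2.2 | about 3.3 |
| 40% | about 2.4 | about 3.7 |

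At 40% the mean delay is about 75 days at 1 per month and 28 days at 4 per month.

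**6. Effect of the SAP threshold.** At 25% the triggers become 3, 5, 7, 9, 11, 13 and 15. Only the first row agrees with the protocol's table.

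**The case against.** **The count could fall.** A DLT must be possibly or probably related. Protocol 5.5.3 lets the investigator revise causality, and some DLT exceptions depend on resolution within 7 days or 72 hours. This stands. A reader might infer that the pause is beyond doubt once the count is reached, and that an early trigger can never raise a false alarm; the documents support that only if no DLT is reclassified.

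**The last row looks inert.** A reader might infer that the 49 row can be deleted because 49 is the phase 2 maximum. The documents do not support this. Protocol 7.1 pools phase 1 subjects into the model, and a 3+3 design leaves 3 to 6 of them at the RP2D. If they count toward the blocks, the 49 look falls after 43 to 46 phase 2 subjects, with 3 to 6 still to enroll.

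**Enrollment may not in fact continue.** No sentence says that it does; this is read from the absence of a hold. The DEC Plan, which is not among the documents, may add review points. Serious events reach the sponsor within 24 hours, and Protocol 5.5.11–5.5.12 and 6.3 allow enrollment or the study to be halted. It would therefore be wrong to say that the trial cannot stop earlier. These powers are discretionary, however, and not tied to the DLT count.

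**The monitoring may be meant as continuous.** Protocol 7.1 speaks of the whole treatment period, but the only schedule it states is by sevens. Applying the posterior afresh after each subject would be a different rule: it would pause on one DLT among the first three subjects.

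**The gain is modest.** Without calendar time, the expected saving at a true rate of 20% is 0.7 subjects (34.2 − 33.5). The rule is also a pause for review, not a stop.

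**Conclusion.** The gap holds: the stated schedule looks only at block ends, and no rule in the protocol or SAP acts on a trigger count reached earlier. In most trials that pause, the count is met before the block's last subject. The cost is about 2 to 4 extra subjects on average, for true rates of 20% to 40%. That size assumes phase 2 subjects only, accrual of 1 to 4 per month, DLT times spread evenly over cycle 1, and no reclassification. The table itself is correct at the protocol's threshold, and pause probabilities of about 0.48, 0.91 and 0.996 are unaffected by the timing.

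This is a modest, cheaply avoided exposure. It does not undermine the safety monitoring as a whole or the Simon design.

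**What to change.** Settle two points first:

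- Reconcile the 20% threshold in Protocol 7.1 and the synopsis with the 25% in SAP 6.2.3, and give one trigger table in both documents.
- State whether phase 1 subjects treated at the RP2D count toward the blocks of seven. Keep the 49 row unless only phase 2 subjects are counted.

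Then add to Protocol 7.1, the synopsis, SAP 6.2.3 and the DEC Plan:

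- Enrollment is paused and the DEC convened as soon as the cumulative number of confirmed DLTs reaches the table value for the block being filled.
- The scheduled looks at 7, 14, 21 and so on remain, for estimating the DLT rate.
- If the DEC allows enrollment to resume at the same dose, the next check uses the next row.

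The cost is a short amendment, an occasional unscheduled DEC meeting, and a rare early pause for a DLT that is later reclassified. No extra subjects or data are needed, and the Simon boundaries do not change.

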7.2 Analysis Sets

Detailed criteria for analysis sets will be laid out in Classification Specifications and the allocation of subjects to analysis sets will be determined prior to database hard-lock.

7.2.1 Full Analysis Set (FAS)

The full analysis set (FAS) will consist of all subjects who are enrolled in the study and took at least 1 dose of study drug. The FAS will be used for efficacy analyses. Subjects will be analyzed based on the actual treatment received.

7.2.2 Per Protocol Set (PPS)

The per protocol set (PPS) will consist of the subset of the FAS who do not meet criteria for PPS exclusion. These criteria are to capture relevant non-adherence to the protocol and will be defined in the SAP. The sensitivity analyses for the primary and some secondary endpoints may be performed on the PPS. Select demographic and baseline characteristics will also be summarized for the PPS.

7.2.3 Safety Analysis Set (SAF)

For the statistical summary of the safety data, the safety analysis set (SAF) will be used. The SAF consists of all subjects who took at least 1 dose of study drug (gilteritinib or atezolizumab) and will be used for safety analyses. The subjects will be analyzed based on the actual treatment received. The FAS and SAF are the same for this study.

7.2.4 Pharmacokinetics Analysis Set (PKAS)

The pharmacokinetics analysis set (PKAS) consists of the administered population for which sufficient plasma concentration data is available to facilitate derivation of at least one pharmacokinetic parameter and for whom at least 1 plasma concentration datum is available and both the date and time of dosing on the day of pharmacokinetic sampling and the date and time of sampling are known. Additional subjects may be excluded from the PKAS at the discretion of the pharmacokineticist. Any formal definitions for exclusion of subjects or time-points from the PKAS will be documented in the in the Classification Specifications and determined the Classification Meeting.

7.2.5 Biomarker Analysis Set (BMAS)

The biomarker analysis set (BMAS) will include the subjects from the administered population for whom sufficient biomarker measurements were collected.

7.3 Demographics and Baseline Characteristics

7.3.1 Demographics

Demographics and baseline characteristics will be summarized by treatment group for the SAF. Descriptive statistics will include number of subjects, mean, standard deviation, minimum, median and maximum for continuous endpoints and frequency and percentage for categorical endpoints.

7.3.2 Subject Disposition

The number and percentage of all subjects during the study will be reported per treatment group, study drug administration, subject completion, premature discontinuation and major protocol violations.

7.3.3 Previous and Concomitant Medications

The frequency of concomitant medications (prescription, over-the-counter and nutritional supplements) will be summarized by treatment group and PT for SAF. Medications will be coded using the WHO drug dictionary. Medications will be counted by the number of subjects who took each medication. A subject taking the same medication multiple times will only be counted once for that medication. Medications will be presented in decreasing order of frequency based on the total number of subjects who took each medication.

7.3.4 Medical History

A detailed medical history for each subject will be obtained during screening period and will be summarized by treatment group for the SAF

7.3.5 Disease History

Each subject's complete cancer history will be listed. The number and percentage of subjects will be used to summarize the AML subtype and FLT3 mutation status.

7.3.6 Treatment Compliance

Treatment compliance is defined as the total number of doses of gilteritinib in combination with atezolizumab actually taken by the subject divided by the number of doses of study drug expected to be taken during the study multiplied by 100. Descriptive statistics for study drug compliance will be presented by dose for the entire study period for the SAF by treatment group.

7.3.7 Extent of Exposure

Drug exposure including duration of exposure, cumulative dose, average daily dose, dose intensity and relative dose intensity will be summarized by treatment group. The number and

proportion of subjects with dose reduction, dose escalation and dose interruption will be tabulated. Details of the calculation will be provided in SAP.

7.4 Analysis of Efficacy

Efficacy analysis will be conducted on the FAS and PPS in which FAS will be considered as primary and PPS as supportive.

7.4.1 Analysis of Efficacy Variables

CRc rate, CR rate, best response rate, duration of remission, EFS and OS, will be summarized using descriptive statistics. The CRc rate, CR rate, best response rate with the corresponding 95% confidence interval will be reported by treatment group. The survival curve and median time for time-to-event variables will be estimated using the Kaplan-Meier method and will be reported along with the corresponding 95% confidence interval by treatment group.

7.5 Analysis of Safety

The safety evaluation will be based mainly on AEs, clinical laboratory results, vital sign measurements, ECGs and ECOG performance scores. Descriptive statistics will be used to summarize safety data. All safety data will be summarized by treatment received and the analyses will be performed on the SAF.

7.5.1 Adverse Events

All AEs recorded on treatment including within 30 days from the last study treatment will be summarized. AEs will be categorized by SOC and PT using the MedDRA dictionary and will be graded according to the NCI CTCAE version 5.0.

The number and percent of subjects experiencing 1 or more AE(s) will be summarized by treatment group, SOC and PT. The number and percentage of subjects with at least one grade 3 or higher AE will be summarized by treatment group, SOC and PT.

Distribution of the maximum severity (grade) and treatment-related AEs will be summarized by treatment group, SOC and PT. Distribution of SAEs, discontinuations due to AE and deaths on study will be presented for each treatment group.

Additional summary tables will be generated for the following population subsets: subjects with SAEs including deaths, subjects who discontinue due to AEs and investigator-attributed relationship to study drug for AEs and SAEs.

All summaries of AEs will include only TEAEs unless otherwise stated. Listings of AEs, SAEs, deaths and withdrawals due to AEs will be presented.

7.5.2 Laboratory Assessments

Clinical laboratory evaluations (including serum chemistry, hematology, coagulation and urinalysis) and their changes from baseline will be summarized by treatment group using descriptive statistics. Clinically significant abnormalities in laboratory values will be presented for each treatment. Shift tables will present shift from baseline to worst grade for

selected variables using the NCI-CTCAE grade and laboratory reference range indicator. Frequency of subjects with laboratory values outside normal range will be generated in addition to tabulation of worst toxicity grade.

7.5.3 Vital Signs

Descriptive statistics will be used to summarize vital sign results and changes from baseline by treatment group and time point.

7.5.4 Physical Examination

Physical examination findings will be listed by the actual treatment received. All clinically significant abnormal findings will be recorded as medical history or AEs and graded using NCI-CTCAE guidelines.

7.5.5 Routine 12-lead Electrocardiograms

The 12-lead ECG results will be summarized by the actual treatment received and time point. Overall ECG interpretation will be summarized for each time point. A shift analysis table showing shifts from baseline in overall ECG (normal, abnormal) will be provided. ECG parameters and their change from baseline will be summarized by treatment group using descriptive statistics.

7.6 Analysis of Pharmacokinetics

Descriptive statistics (e.g., N, mean, standard deviation, minimum, median, maximum, coefficient of variation [CV], geometric mean, and geometric CV) will be provided for trough plasma concentrations (C_{trough}) of gilteritinib and possible metabolite(s), if appropriate, by treatment, visit and time point.

7.7 Analysis of Pharmacodynamics

Changes in the activation status of FLT3 and AXL may be assessed before and after treatment.

7.8 Analysis of Biomarkers

MRD will be assessed in relation to the following efficacy variables: CRc rate, CR rate, EFS, Duration of remission and OS.

FLT3 mutational status at baseline and EOT, as well as mutations in other AML related genes and protein expression will be assessed in relation to CRc rate, CR rate, EFS, Duration of remission and OS.

Baseline levels and changes from baseline in immune cell populations and AML blasts by immunophenotyping will be assessed in relation to CRc rate, CR rate and OS.

7.9 Major Protocol Deviations and Other Analyses

Major protocol deviations as defined in [[Section 8.3 Major Protocol Deviations](#)] will be provided in a data listing.

The major protocol deviation criteria will be uniquely identified as follows:

PD1 - Entered into the study even though they did not satisfy entry criteria,

PD2 - Developed withdrawal criteria during the study and was not withdrawn,

PD3 - Received wrong treatment or incorrect dose,

PD4 - Received excluded concomitant treatment.

